11.1 Types

Any unfavorable and unintended sign (abnormal and clinically significant analytical result), associated or not with the use of drugs, will be assessed as an adverse event.

11.2 Serious Adverse Events

Information on Serious Adverse Events (AAG) and Unexpected Serious Adverse Reactions (RAGI) with suspected causal relationship with the treatments under study, will be collected and recorded in the notification form of Serious Adverse Events (RD223 / 2004). Such serious adverse events must also be notified to the AEMPS, which will be done from the ESIC and for this the investigator must notify it within 24 hours of its knowledge. Only serious, unexpected AAs related to the treatments under study will be reported to the AEMPS.

AAG or RAGI is considered any adverse event or adverse reaction at any dose:

- Produce death of patients,
- Threatens the subject's life,
- Make necessary the hospitalization of the subject or the prolongation of it,
- Produces disability or permanent or significant disability, or
- Lead to an abnormality or congenital malformation.

The intensity of AA will be classified as mild, moderate or severe. The researcher will record the relationship of the study product with the AA according to the following causality terms:

- Related: the AA follows a reasonable time sequence from the moment of exposure to the product. It can not be explained by the clinical condition of the subject or by the procedures / conditions of the study. AA decreases after discontinuation of the study product and reappears once the study product is re-administered.
- Possibly related: the AA follows a reasonable temporal sequence from the moment of exposure to the product, but it may have been caused by the clinical condition of the subject or by the procedures / conditions of the study.
- Improbably related: the temporal association between the AA and the product of the study is such that it is unlikely that there is any reasonable relationship between them. The relationship is not likely due to other possible explanations.
- Not related: the AA, without a doubt, has been caused by the clinical condition of the subject or by the procedures / conditions of the EC. A reasonable explanation must be given, for example, that the product under investigation or an incompatible temporal relationship has not been consumed.

- Not evaluable: the report that indicates an adverse reaction can not be judged because the information that is counted is insufficient or contradictory, and no extra data can be added or the existing ones can be verified.

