9.6.2 Security Reports

The promoter must be informed immediately of all serious adverse events, except those that are specified in the protocol or other document. It will be reported quickly, in writing, in detail and in the time periods specified by the promoter in the protocol. These follow-up reports must identify the subjects by means of the codes assigned in the CB and not by the names of the subjects, personal identification numbers and / or addresses.

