11 ADVERSE EVENTS

The Adverse Events (AA) produced during the study will be evaluated. An AA is defined as any harmful event in a patient after randomization and during the performance of a study, even if it is considered not to be related to the treatment of the study. In this CE, the AAs in the CRD will be collected and recorded, as long as they are serious (if they cause clinical signs or symptoms and are considered clinically significant).

Diseases or medical conditions that were present before administering the product under study, will only be considered as AA if there is a worsening after the start of the study intervention (any procedure specified in the protocol).

To the extent possible, AAs will be described based on:

- Duration (start and end dates).

- Degree of severity (mild, moderate, severe).
- Relationship with the study medication (suspected / not suspected).
- Action (s) taken to correct it.

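### Section 11.2 gives two inconsistent rules for notifying the agency, and on one reading its serious event form covers fewer events than section 9.6.2 wants reported to the sponsor.

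*Protocol*

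**What the plan says.** Four parts of the protocol govern what happens to a serious event.

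- **Section 11 (definition and CRD).** An adverse event counts "even if it is considered not to be related to the treatment of the study". Serious ones are entered in the CRD, with relationship coded as suspected or not suspected. No causal condition is attached to that entry.
- **Section 11.2 (form and agency).** The sentence that sets the scope of the form names serious adverse events (AAG) and then unexpected serious reactions (RAGI), and continues "with suspected causal relationship with the treatments under study, will be collected and recorded in the notification form of Serious Adverse Events". On the agency, the section first says "Such serious adverse events must also be notified to the AEMPS", to be done from a body called ESIC, for which "the investigator must notify it within 24 hours of its knowledge". It then says "Only serious, unexpected AAs related to the treatments under study will be reported to the AEMPS". The same section lists the causality terms the investigator records, among them improbably related and not related.
- **Section 9.6.2 (sponsor).** "The promoter must be informed immediately of all serious adverse events, except those that are specified in the protocol or other document". Reports must keep to time periods that the protocol is said to specify.
- **Sections 7.2 and 7.4 (variables and endpoints).** The adverse event variable and the adverse event rate listed there are both confined to events attributed to treatment (7.2 adds those attributed to study recommendations).

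Annex 3 supplies the form. Its heading refers to serious adverse events, but the title box inside it, in Spanish, refers to a suspected adverse reaction.

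**The concern.** Safety of the supplement is a secondary objective, and the trial is placebo-controlled and double-blind. Prompt reporting of serious events should therefore not depend on whether the site believes the capsule was responsible.

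In patients with a stent, an admission for obstruction or infection is easily put down to the underlying condition, and that is how section 11.2 describes its not-related category. If causality decides whether an event goes on the form, the sponsor may not hear quickly of the very events that sites tend to explain away. Separately, a site that tries to follow section 11.2 on agency notification meets two instructions that do not agree.

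**Working it through.** No arithmetic applies: the point rests on no sample size, rate or power figure. The check is to sort serious events into three classes and see what each rule does with them.

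The causal condition in the form sentence can be parsed in two ways:

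- **Narrow:** it governs both serious adverse events and unexpected serious reactions.
- **Wide:** it governs only the unexpected reactions, the term immediately before it.

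| Rule | Related, unexpected | Related, expected | Judged unrelated |
|---|---|---|---|
| CRD (section 11) | yes | yes | yes |
| To sponsor at once (9.6.2, subject to its exception) | yes | yes | yes |
| Form, narrow reading (11.2) | yes | yes | **no** |
| Form, wide reading (11.2) | yes | yes | yes |
| Agency, first sentence, narrow reading | yes | yes | no |
| Agency, first sentence, wide reading | yes | yes | yes |
| Agency, second sentence | yes | **no** | **no** |
| Adverse event variable and rate (7.2, 7.4) | yes | yes | no |

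**Agency rules.** On the narrow reading the two sentences disagree about one class, related and expected. On the wide reading they disagree about two, because the first sentence then also takes in unrelated events. The second rule is a subset of the first, so the conflict exists on both readings.

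**Form against 9.6.2.** The rules disagree only on the narrow reading, and only for events judged unrelated. The title box of the Annex 3 form favours that reading: an investigator holding a sheet labelled for suspected reactions could reasonably conclude that an unrelated event does not belong on it.

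**Exception in 9.6.2.** The duty to inform the sponsor excludes events specified in the protocol or another document. Nothing in the protocol expressly exempts unrelated serious events. A reader could take 11.2 itself as the exemption, which makes the position less clear.

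**Deadline.** Section 9.6.2 says immediately and also defers to periods given in the protocol. The only numeric period is the 24 hours in 11.2. That period hangs on the first agency sentence and on ESIC, which is defined nowhere and is not linked to the sponsor or to the monitoring CRO. On the narrow reading it does not reach unrelated events.

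**The case against.** The strongest reply is that little is lost. Section 11 puts serious events in the CRD whatever their cause, and 11.2 keeps a not-related code that calls for a reasoned explanation. A serious event is also a discontinuation criterion in 6.2.3, and 7.2 collects stent complications, emergency visits and hospitalizations. A comparison of arms would draw on the CRD; nothing makes the form the source for analysis.

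The wide reading is also fair grammar. The sentence names serious adverse events separately from unexpected reactions, and the causality list that follows would have less purpose if unrelated events were out of scope. The second agency sentence may simply be meant to limit the first. Section 9.6.2 already gives a recipient, the sponsor, and a time.

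Most of this stands, and it rules out three stronger conclusions that a reader might draw:

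- *Serious events judged unrelated go unrecorded.* Section 11 and the causality codes contradict this.
- *The two agency rules are opposites.* The second is a narrower version of the first; they are inconsistent.
- *An unrelated serious event has no recipient.* Section 9.6.2 names the sponsor.

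The reply does not remove the agency conflict, since no wording marks the second sentence as limiting the first. Nor does it settle which events belong on the form. CRD capture is also not the same as prompt notification, and the adverse event variable and rate in 7.2 and 7.4 carry a causal filter of their own. The analysis plan, which is not at hand, may tabulate more than the protocol lists.

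**Conclusion.** The point holds as an inconsistency in the safety-reporting rules that the sponsor should correct. It does not show that data are lost, and it does not touch the primary efficacy comparison.

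The conflict between the two agency sentences rests on no assumption about parsing. The mismatch between the form and 9.6.2 rests on the narrow reading of 11.2, which is natural and fits the Annex 3 title box but is not the only one. On that reading, serious events judged unrelated may miss the form and the 24-hour route while still being entered in the CRD.

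The size cannot be put as a number of events. The protocol states neither a serious event rate nor how often sites would judge such events unrelated, and any count would be invented.

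**What to change.** Reconcile sections 9.6.2, 11 and 11.2:

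1. State in 11.2 that every serious adverse event, whatever its causality or expectedness, goes on the form and to the sponsor. Align the title box of the Annex 3 form.
2. Give one deadline for that report and say whether the 24 hours is meant to be it. Replace or define ESIC so that the recipient is named.
3. State any exception under 9.6.2 explicitly, or remove the clause.
4. Keep a single agency rule, the unexpected and suspected-related subset already in the second sentence of 11.2, applied after causality and expectedness have been assessed. Delete or reword the first sentence.
5. Say that all serious events will be tabulated by arm regardless of attribution, alongside the attributable-event rate in 7.4.

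The cost is a few sentences and a handful of extra forms for events judged unrelated. No dose, visit or aspect of patient care changes.

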11.3 Action taken and resolution of AA

The researcher will record the action / s taken with the product and the effects of the event for each of the AAs, according to the following:

- Action taken in relation to the product.
- Resolution.

11.4 Follow up with AA

Patients can be withdrawn from the EC at any time. Patients withdrawn from the study due to an AA should be followed up by the investigator until the clinical outcome of the AA is determined.

ANNEX 1: DECLARATION OF HELSINKI

DECLARATION OF HELSINKI OF THE WORLD MEDICAL ASSOCIATION

Ethical principles for medical research in humans

Adopted by the 18th World Medical Assembly, Helsinki, Finland, June 1964 and amended by the

29th World Medical Assembly, Tokyo, Japan, October 1975

35th World Medical Assembly, Venice, Italy, October 1983

41st World Medical Assembly, Hong Kong, September 1989

48th General Assembly Somerset West, South Africa, October 1996

52nd General Assembly, Edinburgh, Scotland, October 2000

Clarification Note of Paragraph 29, added by the General Assembly of the AMM,

Washington 2002

Clarification Note of Paragraph 30, added by the General Assembly of the AMM,

Tokyo 2004

59th General Assembly, Seoul, Korea, October 2008

64th General Assembly, Fortaleza, Brazil, October 2013.

Introduction

1. The World Medical Association (AMM) has promulgated the Declaration of Helsinki as a proposal of ethical principles for medical research in humans, including the investigation of identifiable human material and information.

The Declaration should be considered as a whole and a paragraph should be applied with consideration of all other relevant paragraphs.

2. In accordance with the mandate of the AMM, the Declaration is intended primarily for physicians. The AMM urges others involved in medical research in humans to adopt these principles.

General principles

3. The Geneva Declaration of the World Medical Association links the doctor with the formula "carefully and above all for the health of my patient", and the International Code of Medical Ethics states that: "The doctor must consider what is best for him. patient when giving medical attention. "

4. The duty of the doctor is to promote and ensure the health, welfare and rights of patients, including those involved in medical research. The knowledge and conscience of the doctor must be subordinated to the fulfillment of that duty.

5. The progress of medicine is based on research that, ultimately, must include studies on human beings.
6. The main purpose of medical research in humans is to understand the causes, evolution and effects of diseases and improve preventive, diagnostic and therapeutic interventions (methods, procedures and treatments). Even the best tested interventions must be continually evaluated through research to be safe, effective, accessible and of quality.
7. Medical research is subject to ethical standards that serve to promote and ensure respect for all human beings and to protect their health and their individual rights.
8. Although the main objective of medical research is to generate new knowledge, this objective should never have primacy over the rights and interests of the person participating in the research.
9. In medical research, it is the doctor's duty to protect life, health, dignity, integrity, the right to self-determination, privacy and confidentiality of personal information of people who participate in research. The responsibility for the protection of the persons taking part in the investigation must always rest with a doctor or other health professional and never with the participants in the research, even if they have given their consent.
10. Physicians should consider the ethical, legal and legal norms and standards for human research in their own countries, as well as current international standards and norms. A national or international ethical, legal or legal requirement should not be allowed to diminish or eliminate any measure of protection for persons participating in the research established in this Declaration.
11. Medical research should be conducted in a manner that minimizes possible harm to the environment.
12. Medical research in human beings should be carried out only by persons with appropriate education, training and scientific and ethical qualifications. Research on healthy patients or volunteers requires the supervision of a physician or other appropriately qualified and qualified health professional.
13. Groups that are underrepresented in medical research must have appropriate access to participation in research.
14. The physician who combines medical research with medical care should involve his patients in the investigation only to the extent that this demonstrates a justified potential preventive, diagnostic or therapeutic value and if the doctor has good reason to believe that the participation in the study it will not adversely affect the health of those who take part in the research.
15. Appropriate compensation and treatment must be ensured for people who are injured during their participation in the investigation.

Risks, Costs and Benefits

16. In the practice of medicine and medical research, most interventions involve some risks and costs.

Medical research in humans should only be carried out when the importance of its objective is greater than the risk and the costs for the person participating in the research.

17. All medical research on human beings should be preceded by a careful comparison of the risks and costs for the individuals and groups involved in the research, compared to the foreseeable benefits for them and for other persons or groups affected by the research. the disease that is investigated.

Measures must be implemented to minimize risks. The risks must be monitored, evaluated and documented continuously by the researcher.

18. Physicians should not be involved in research studies in humans unless they are sure that the risks have been adequately evaluated and that they can be satisfactorily addressed.

When the risks involved are more important than the expected benefits or if there is conclusive evidence of definitive results, physicians should evaluate whether they continue, modify or suspend the study immediately.

Groups and vulnerable people

19. Some groups and individuals under investigation are particularly vulnerable and may be more likely to suffer abuse or additional harm.

All groups and individuals must receive specific protection.

20. Medical research in a vulnerable group is only justified if the research responds to the health needs or priorities of this group and the research can not be carried out in a non-vulnerable group. In addition, this group can benefit from the knowledge, practices or interventions derived from the research.

Scientific requirements and research protocols

21. Medical research in human beings must comply with generally accepted scientific principles and should be based on a thorough knowledge of the scientific literature, other pertinent sources of information, as well as on properly performed laboratory experiments and on animals, when appropriate. . The welfare of the animals used in the experiments must also be taken care of.

The project and the method of all study in human beings must be clearly described and justified in a research protocol.

22. The protocol should always refer to the ethical considerations that are relevant and should indicate how the principles enunciated in this Declaration have been considered. The protocol should include information on financing, sponsors, institutional affiliations, possible conflicts of interest and incentives for people in the study and information on the stipulations to treat or compensate people who have suffered damages as a result of their participation in the research.

In clinical trials, the protocol should also describe the appropriate arrangements for stipulations after the trial.

Research ethics committees

23. The research protocol should be sent for consideration, comment, advice and approval to the relevant research ethics committee before beginning the study. This committee must be transparent in its operation, must be independent of the investigator, the sponsor or any other type of undue influence and must be properly qualified. The committee must consider the laws and regulations in force in the country where the research is being carried out, as well as the

international standards in force, but they should not be allowed to diminish or eliminate any of the protections for the persons participating in the research established in this Declaration.

The committee has the right to control ongoing trials. The investigator has the obligation to provide control information to the committee, especially any serious adverse incident. No amendment to the protocol should be made without the consideration and approval of the committee. After the study ends, researchers must submit a final report to the committee with a summary of the results and conclusions of the study.

Privacy and confidentiality

24. All precautions must be taken to safeguard the privacy of the person participating in the investigation and the confidentiality of their personal information.

Informed consent

25. The participation of persons capable of giving informed consent in medical research must be voluntary. Although it may be appropriate to consult relatives or community leaders, no person able to give informed consent should be included in a study, unless they freely accept it.

26. In medical research on human beings capable of giving their informed consent, each potential individual must receive adequate information about the objectives, methods, sources of financing, possible conflicts of interest, institutional affiliations of the researcher, calculated benefits, foreseeable risks and discomforts derived from the experiment, post-study stipulations and all other pertinent aspects of the research. The potential person must be informed of the right to participate or not in the investigation and to withdraw their consent at any time, without exposing themselves to reprisals. Special attention must be paid to the specific information needs of each potential individual, as well as to the methods used to deliver the information.

After making sure that the individual has understood the information, the doctor or other appropriately qualified person should then request, preferably in writing, the informed and voluntary consent of the person. If the consent can not be granted in writing, the process to achieve it must be documented and formally attested.

All people who participate in medical research should have the option of being informed about the overall results of the study.

27. When requesting informed consent for participation in the research, the physician must take special care when the potential individual is linked to him by a dependency relationship or if he consents under pressure. In such a situation, informed consent must be requested by a properly qualified person who has nothing to do with that relationship.

28. When the potential individual is unable to give informed consent, the physician must request the informed consent of the legal representative. These people should not be included in the research that has no possibility of benefit for them, unless it aims to promote the health of the group represented by the potential individual and this research can not be carried out on people capable of giving their informed consent and research involves only minimal risk and cost.

29. If a potential individual participating in the research considered unable to give informed consent is able to agree to participate or not in the investigation, the doctor must request it, in addition to the consent of the legal representative. The disagreement of the potential individual must be respected.

30. Research on individuals who are not physically or mentally able to give consent, for example, unconscious, can be done only if the physical / mental condition that prevents the granting of informed consent is a necessary characteristic of the group investigated. In these circumstances, the doctor must request informed consent from the legal representative. If such a representative is not available and if the investigation can not be delayed, the study can be carried out without informed consent, provided that the specific reasons for including individuals with a disease that does not allow them to give informed consent have been stipulated in the protocol. of the research and study has been approved by a research ethics committee. Consent to stay in the investigation must be obtained as soon as possible from the individual or a legal representative.

31. The physician must thoroughly inform the patient about aspects of the care that are related to the investigation. The refusal of the patient to participate in an investigation or his decision to withdraw should never adversely affect the doctor-patient relationship.

32. For medical research using identifiable human material or data, such as research on material or data contained in biobanks or similar repositories, the physician must request informed consent for collection, analysis, storage and reuse. There may be exceptional situations in which it will be impossible or impracticable to obtain consent for such an investigation. In this situation, the investigation can only be conducted after being considered and approved by a research ethics committee.

Use of placebo

33. The possible benefits, risks, costs and effectiveness of any new intervention should be evaluated by comparing it with the best interventions tested, except in the following circumstances:

When there is no proven intervention, the use of a placebo, or no intervention, is acceptable or

When for methodological, scientific and compelling reasons, the use of any intervention less effective than the best tested, the use of a placebo or no intervention is necessary to determine the efficacy and safety of an intervention.

and who receive any less effective intervention than the best tested, placebo or no intervention, will not run additional risks, serious adverse effects or irreversible damage as a result of not receiving the best intervention tested.

Great care must be taken to avoid abusing this option.

Post-test stipulations

34. Before the clinical trial, sponsors, researchers and host governments should provide post-trial access to all participants who still need an intervention that has been identified as beneficial in the trial. This information should also be provided to participants during the informed consent process.

Registration and publication of research and dissemination of results

35. Any research study with human beings should be recorded in a database available to the public before accepting the first person.

36. Researchers, authors, sponsors, editors and directors all have ethical obligations regarding the publication and dissemination of the results of their research. Researchers have a duty to

make the results of their research available to the public and they are responsible for the integrity and accuracy of their reports. All parties must accept the ethical standards of information delivery. Negative and inconclusive results must be published as well as positive results or otherwise they must be available to the public. The publication should mention the source of financing, institutional affiliations and conflicts of interest. Reports on investigations that do not conform to the principles described in this Declaration should not be accepted for publication.

Interventions not proven in clinical practice

37. When in the care of a patient the proven interventions do not exist or other known interventions have been ineffective, the doctor, after asking expert advice, with the informed consent of the patient or an authorized legal representative, can afford to use interventions not proven, if, in his opinion, it gives any hope of saving life, restoring health or alleviating suffering. Such interventions should be further investigated in order to assess their safety and efficacy. In all cases, this new information must be recorded and, when appropriate, made available to the public.

